### 9.2 Definition of Serious Adverse Events

Each AE is to be classified by the Investigator as either serious or non-serious. This classification of the seriousness of the AE determines the reporting procedures to be followed. An AE that meets one or more of the following criteria/outcomes should be classified as serious:

- It is fatal or life-threatening.

---

 The term “life-threatening” in the definition of “serious” refers to an event in which the patient, in view of either the Investigator or the Sponsor, was at risk of death at the time of the event; it does not refer to an event that hypothetically might have caused death if it were more severe. Death alone is not considered an AE; it is an outcome of an AE. Reports of death should be accompanied by the corresponding AE term for the event that led to death. However, sudden death or death due to unexplainable cause should be reported as an SAE, while follow-up is pursued to determine the cause.

- It requires inpatient hospitalization or prolongation of existing hospitalization.
- It results in persistent or significant disability/incapacity.
- It is a congenital anomaly/birth defect.
- It is a medically important event.

### 9.3 Definition of Non-serious Adverse Events

A non-serious AE is any AE that does not fulfil the definition of an SAE.

### 9.4 Definition of Predefined Adverse Events of Special Interest

The following AEs (serious and non-serious) graded according to CTCAE v5.0 Revised CRS Criteria according to Lee et al. for CRS are selected as adverse events of special interest (AESIs) in this trial:

- CRS grade 2 or higher
- Hypotension grade 3 or higher not in connection with CRS
- Neuralgia grade 3 or higher
- Peripheral neuropathy grade 3 or higher

---

 Hospitalization is defined as admission to a hospital/inpatient stay (irrespective of the duration of the physical stay) or no admission to a hospital/no inpatient stay but stay at the hospital for treatment or observation for more than 24 h. Events leading to hospitalizations for the following reasons should not be reported as SAEs:

[figure not shown]
- Trial-related purposes not associated with any deterioration in the condition
- Social reasons in the absence of any deterioration in the patient's general condition
- Elective surgery or other scheduled hospitalization periods that were planned before the patient was included in this trial.

 Medical and scientific judgment must be exercised in deciding whether an AE is believed to be "medically important." Medically important events may not be immediately life-threatening or result in death or hospitalization but may jeopardize the patient or may require intervention to prevent one of the other outcomes listed in the SAE definition above.

## 9.5 Adverse Event Reporting Period

The AE reporting period is shown in [Figure 9-1](#).

**Figure 9-1 Adverse event reporting**

**Abbreviations:** AE = adverse event; AESI = adverse events of special interest; IMP = investigational medicinal product; SAE = serious adverse event

### 9.5.1 Non-serious Adverse Events Reporting

Non-serious AEs (including non-serious AESIs) should be reported from signing informed consent until 30 days after the last IMP administration.

### 9.5.2 Serious Adverse Events Reporting

Serious AEs should be reported from signing the informed consent until 30 days after the last IMP administration.

### 9.5.3 Adverse Events During Follow-Up

During the follow-up period, SAEs at least possibly related to nivatrotamab or to the study procedures and new onset of secondary malignancies regardless of causality, should be reported until end of the trial.

### 9.5.4 Adverse Events with Onset After End-of-trial

If the Investigator becomes aware of an SAE after the end of the trial with a suspected causal relationship to the IMPs, it should immediately be reported to the Sponsor.

## 9.6 Recording of Adverse Events

All events meeting the definition of an AE must be collected and reported in the eCRF. SAEs, DLTs, and AESIs (whether serious or non-serious) should be reported both in the eCRF and on the clinical AE report form.

During each contact with the trial site staff, the patient must be asked about AEs, for example, by asking: “Have you experienced any problems since the last contact?” All AEs, observed by the Investigator or the patient, must be reported by the Investigator and evaluated unless specifically excluded (see section 9.6.4).

### **9.6.1 Diagnosis**

The Investigator should report the diagnosis, if available. If no diagnosis is available, the Investigator should record each sign and symptom as individual AEs using separate AE forms.

Further instructions on the recording of CRS and neurological AEs are provided below.

#### **9.6.1.1 Cytokine release syndrome**

AEs that are considered to be consistent with CRS should be recorded as “cytokine release syndrome” on the AE page of the eCRF. Associated signs and symptoms should be recorded on the dedicated CRS eCRF. Cytokine Release Syndrome grade 2 or higher should also be reported as an AESI and CRS grade 3 or higher should be reported as a DLT.

The severity grading of AEs of CRS should be performed in accordance with the CRS grading scheme presented in [Table 7-2](#) in section 7.

#### **9.6.1.2 Neurological Adverse Events**

Neurological AEs (e.g., seizures) should be assessed and graded as per CTCAE version 5.0. The Investigator should indicate in the eCRF if the event is considered to be a symptom of ICANS. ICANS grade 3 or higher should also be reported as a DLT.

### **9.6.2 Onset Date and Time**

Start date for an (S)AE is the date of occurrence of the first symptom. As a minimum, the time should be entered if the event starts on a dosing day of IMP or if the duration of the event is less than 24 h.

### **9.6.3 End Date and Time**

The end date should be filled in if the outcome of an AE is fatal, recovered/resolved, or recovered/resolved with sequelae. The end time should be entered for all events for which start time should be entered, i.e., if the event starts on a dosing day or if the duration of the event is less than 24 h.

### **9.6.4 Signs and Symptoms of the Cancer Disease**

Signs and symptoms which, according to the Investigator, are expected and well-known consequences of the indication both in intensity and frequency, should not be reported as AEs or SAEs except for events with a fatal outcome. Any unexpected change in the intensity or frequency should be reported as an AE or SAE as applicable. In addition, all deaths (including death caused by PD and secondary cancers) must be reported as SAE.

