## 5.2 Endpoints

### 5.2.1 Primary Endpoints

##### Phase 1

- The MTD (defined by an mBOIN design) and the RP2D of nivatrotamab
- The overall incidence and severity of AEs for different doses of nivatrotamab

##### Phase 2

- Incidence and severity of AEs for nivatrotamab dosed at the RP2D

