### 6.2.1.3 Dose Escalation Stages

The dose escalation phase will consist of 2 stages: the initial accelerated titration stage followed by a standard titration stage (Figure 6-1).

In the accelerated titration stage, patients will be recruited and treated in single-patient cohorts. These single-patient cohorts may optionally be expanded with up to 2 additional patients for the purpose of obtaining additional PK and/or pharmacodynamic data.

The initial accelerated titration stage will end, and the single-patient cohort mandatorily expanded with (at least) 2 additional patients once either:

- Dose level 3 is reached, or
- During the DLT evaluation period (28 days), a patient is observed with:
  - any grade  $\geq 2$  AE (excluding toxicities clearly related to disease progression or intercurrent illness), or
  - a protocol defined DLT (section 6.2.3).

whichever occurs first

This will mark the end of the accelerated titration stage and the beginning of the standard titration stage. Hereafter, patients will be allocated to dose-levels typically in cohorts of 3. As the mBOIN design allows cohort-sizes to vary, the actual cohort sizes may differ from 3.

In the standard titration stage, cohorts will be allowed to include only 2 patients who are evaluable for DLT, provided that none of the 2 patients have experienced any related, grade  $\geq 3$  AE during the DLT evaluation period.

If patients are withdrawn prematurely without having experienced a DLT, they will be considered non-evaluable and may be replaced.

In cohorts that include more than 1 patient in the dose escalation part, there will be sequential enrolment. At a particular dose level, there must be at least 3 days between the first dose of the first patient and the first dose of the subsequent patients in the same cohort.

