### 6.2.3 Definition of Dose-limiting Toxicity

DLTs include the following events:

Clinically significant AE (CTCAE version 5.0) or a significant laboratory abnormality (as defined below) that occurs during the DLT assessment period, excluding toxicities clearly related to disease progression or intercurrent illness. The established external, independent DMC will evaluate relatedness of an event in order for it to qualify for a DLT or not.

DLT criteria will be categorized as follows:

1. Thrombocytopenia grade 3 with clinically significant bleeding and neutropenia (i.e., myelosuppression) > grade 3, excluding neutropenia lasting <7 days and
2. Non-hematological toxicities  $\geq$  grade 3, defined as
  - a. Grade 3 non-hematological laboratory abnormalities requiring medical intervention, which are not mentioned in the list of exceptions below.
  - b. Any non-hematological AE of  $\geq$  grade 3 that is not mentioned in the list of exceptions below.
3. Death occurring during DLT evaluation period, not related to disease progression or complications or intercurrent illness as determined by the DMC
4. Injection site reaction  $\geq$  grade 3
5. Dose delay of >21 days (failure to recover from any toxicity, which results in delayed dosing of the subsequent dose)
6. CRS grade 3 or higher
7. Immune effector cell-associated neurotoxicity syndrome (ICANS) grade 3 or higher
8. Peripheral sensory neuropathy grade 4
9. Peripheral sensory neuropathy grade 3 with no sign of clinical improvement within 21 days as evaluated by the investigator.
10. Pain grade 3 or higher lasting 24 h or more despite optimal analgesic therapy administered according to the local standard of care
11. Febrile neutropenia

12. Any AST/ALT and bilirubin elevation meeting Hy's law criteria (a,b,c and d)
  - a. ALT or AST elevation  $> 3 \times$  upper limit of normal (ULN)
  - b. Total bilirubin elevation  $> 2 \times$  ULN
  - c. Absence of initial findings of cholestasis
  - d. No other reason to be found i.e. due to infection (i.e. hepatitis), liver disease or other drug effect

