## 7.2.2.2 Pain

Injection of nivatrotamab may be followed by development of neuropathic pain. The clinical manifestations are varied and could involve the abdomen, lower back, and extremities. Pain is expected to develop by onboarding of IMP to GD2, with estimated onset on Day 1-2 after IMP administration. As many patients might already receive opioids and/or medication for neuropathic pain at enrolment, the below recommendations should be considered as a guideline, and treatment accommodated to each patient at the investigators' discretion.

To prevent the development of severe neuropathic pain, the following pre-emptive analgesia with peroral gabapentin is recommended and should be followed (at home) prior to dosing in all cycles:

- 

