## 9 ADVERSE EVENTS

### 9.1 Definition of Adverse Events

An AE is any untoward medical occurrence in a patient administered a pharmaceutical product which does not necessarily have a causal relationship with the treatment.

An AE can, therefore, be any unfavorable and unintended sign (including an abnormal laboratory finding), symptom, or disease temporally associated with the use of a product, whether or not considered related to the product.

An AE includes

- A clinically significant worsening of a concomitant illness
- A laboratory abnormality that is clinically significant, i.e., an abnormality that suggests a disease and/or organ toxicity and is of a severity that requires active management. Active management includes interventional treatment or further investigations, for example, change of medicine dose or more frequent follow-up due to the abnormality.

A pre-existing condition (i.e., a disorder present before the AE reporting period started, which is noted on the medical history/physical examination form) should not be reported as an AE unless the condition worsens or episodes increase in frequency during the AE reporting period.

Diagnostic and therapeutic non-invasive and invasive procedures, such as surgery, should not be reported as AEs. A medical condition for which an unscheduled procedure was performed should, however, be reported if it meets the definition of an AE. For example, an acute appendicitis should be reported as the AE and not the appendectomy.

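### Section 9.6.4 lets the investigator leave symptoms judged expected for SCLC unrecorded even when a drug cause is possible, so overlapping pain can miss the AE endpoint, the grade ≥2 trigger and the DMC

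*Combined protocol and SAP*

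**What the plan says.** Section 9.6.4 addresses signs and symptoms of the cancer. Those which, in the investigator's view, "are expected and well-known consequences of the indication both in intensity and frequency, should not be reported as AEs or SAEs", unless the outcome is fatal. Two limits follow: "Any unexpected change in the intensity or frequency should be reported as an AE or SAE as applicable", and "all deaths (including death caused by PD and secondary cancers) must be reported as SAE". Section 9.6 names 9.6.4 as the exclusion from its rule that all observed AEs are reported and evaluated, so an excluded symptom is left out altogether and is not recorded as unrelated.

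Four other provisions bear on this:

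- Section 9.1 defines an AE as an unfavourable sign, symptom or disease "whether or not considered related to the product".
- Section 5.2.1 makes "The overall incidence and severity of AEs for different doses of nivatrotamab" a phase 1 primary endpoint. The phase 2 primary endpoint is likewise not limited to related events.
- Section 6.2.1.3 ends accelerated titration on any grade ≥2 AE, "excluding toxicities clearly related to disease progression or intercurrent illness". Section 6.2.3 uses the same exclusion for DLTs.
- Section 6.2.3 adds: "The established external, independent DMC will evaluate relatedness of an event in order for it to qualify for a DLT or not".

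Section 7.2.2.2 describes neuropathic pain as a possible effect of nivatrotamab: "The clinical manifestations are varied and could involve the abdomen, lower back, and extremities". It expects onset on Day 1 or 2 after dosing and notes that many patients may already take opioids or neuropathic-pain medication at enrolment.

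**The concern.** The trial is open-label with no control arm, and its primary safety endpoint counts AEs of any cause. An event that is recorded and called unrelated can be re-examined later. An event that is never entered cannot.

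Two different standards apply to the same event. The titration trigger and the DLT definition set aside only toxicity that is clearly due to progression or intercurrent illness, and for DLTs the DMC decides. Section 9.6.4 asks only whether the symptom is expected for the disease, and the treating investigator decides first. No causality assessment is required, and no log of omitted symptoms is described.

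Pain is where this bites. It is a documented drug effect, many patients may already be treated for it at entry, and pain of grade 3 or higher lasting 24 h or more despite optimal analgesia is a DLT criterion. No pain score appears among the legible rows of Tables 3-1 and 3-2 (some rows are blacked out), so pain appears to depend mainly on AE reporting. If such an event is left out, AE incidence is understated, single-patient cohorts may continue when they should be expanded, and a DLT candidate may not reach the DMC.

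**Working it through.** **Text comparison**

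| Provision | What is set aside | Who decides |
|---|---|---|
| 9.1 | Nothing on grounds of cause | – |
| 6.2.1.3 (grade ≥2 trigger) | Toxicity clearly due to progression or intercurrent illness | Not stated in that section |
| 6.2.3 (DLT) | Same | DMC, on relatedness |
| 9.6.4 | Symptom expected for SCLC in intensity and frequency | Investigator |

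A symptom can be expected for SCLC without being clearly caused by it, for example back pain starting the day after a dose. Such an event can pass the 9.6.4 exclusion while failing the exclusion in 6.2.1.3 and 6.2.3.

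**The plan's own figures reproduce**

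- Table 11-1: P(at least one event) = 1 − (1 − p)^N. For p = 10% and N = 30 this is 1 − 0.90^30 = 95.8%, printed as 96%. All 24 cells agree after rounding.
- Appendix 1: with target 0.28, p_saf = 0.65 × 0.28 = 0.182 and p_tox = 1.4 × 0.28 = 0.392, the BOIN boundaries are 0.2285 and 0.3344, printed as 0.229 and 0.334. The Table 6-3 thresholds for 2 to 9 patients follow.

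**Sensitivity (illustration)**

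Let u be the share of true events left unrecorded. The documents give no value for u, so it is an assumption. The recorded rate is q = p(1 − u). Table 6-3 escalates on 0 of 3 or on at most 1 of 6:

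- P(0 of 3) = (1 − q)^3
- P(at most 1 of 6) = (1 − q)^6 + 6q(1 − q)^5

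With p = 0.39, the plan's rounded p_tox:

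| u | q | P(0 of 3) | P(at most 1 of 6) |
|---|---|---|---|
| 0% | 0.390 | 22.7% | 24.9% |
| 10% | 0.351 | 27.3% | 31.7% |
| 20% | 0.312 | 32.6% | 39.5% |
| 30% | 0.273 | 38.4% | 48.0% |

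Here u applies to all DLTs, which overstates the effect of this clause. More exactly, u = (share of DLTs that could pass for SCLC symptoms) × (share of those omitted). If, say, 25% overlap and 20% of those are omitted (both assumptions), u = 0.25 × 0.20 = 5%, q = 0.39 × 0.95 = 0.3705, and P(0 of 3) = 0.6295^3 = 24.9%, against 22.7% with no loss.

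**The other two uses of AE data**

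- Grade ≥2 trigger: with an assumed 50% true rate per patient, two single-patient cohorts pass untriggered with probability (1 − 0.5)^2 = 25%. With u = 20% this becomes (1 − 0.4)^2 = 36%.
- Phase 2, N = 30: for an AE with a 10% true rate, P(at least one recorded) falls from 95.8% to 1 − 0.92^30 = 91.8% at u = 20%.

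Since q is never above p, the direction is fixed: fewer recorded events and more escalation. Only the size is unknown.

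**The case against.** The strongest reply is that the clause is narrow. The symptom must be expected in intensity and in frequency, and an unexpected change is reportable. Section 9.1 makes worsening of a pre-existing condition noted at baseline an AE. Section 9.6.7 provides for an event that follows dosing plausibly but could also come from the patient's clinical state: it is possibly related. Grade ≥3 neuralgia and grade ≥3 peripheral neuropathy are named AESIs, and DLTs and AESIs have 24 h reporting. CRS grading, ICE scores, laboratory tests and ECGs are done on schedule.

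Much of this stands. A reader might infer that any symptom can be dropped, or that overlapping toxicity never reaches the DMC. The documents do not support either reading, for the reasons just given. Nor do they support extending the overlap to fatigue, which appears only as a DLT exception, or to neuropathy in general: no section describes either as a usual SCLC symptom.

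Three parts do not fully answer the point. First, whether a change is unexpected is judged by the same investigator, with no grade criterion, and new pain with no baseline record falls outside the pre-existing-condition rule in 9.1. Second, the AESI and DLT routes are not independent of AE reporting: Section 9.4 defines AESIs as AEs, and Section 6.2.3 opens its DLT definition with a clinically significant AE or laboratory abnormality. Third, the causality categories in 9.6.7 apply to events that are reported.

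On size, the objection is right. CRS, ICANS, febrile neutropenia, Hy's law cases, injection-site reactions, dose delays and deaths could not plausibly be taken for SCLC symptoms. Section 4.6 reports that the two DLTs in the first-in-human trial were syncope and sympathetic neuropathy with orthostatic hypotension, with no severe pain.

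**Conclusion.** The point holds in a limited form. Section 9.6.4 allows a non-fatal symptom judged expected for SCLC to go unrecorded although a drug cause is possible. This conflicts with 9.1 and with the cause-neutral AE endpoints. It is looser than the exclusion in 6.2.1.3 and 6.2.3, and it pre-empts the DMC's judgement of DLT relatedness. The overlap that the documents establish is pain, including neuropathic pain.

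The bias is toward fewer recorded AEs and more escalation. Its size cannot be derived from the documents. The rise from 23% to 38% in P(0 of 3) assumes that up to 30% of all DLTs go unrecorded, which is more than this clause could plausibly cause. A reader might run the escalation rules forward at such rates and read off a probability of selecting too high an MTD. That would not measure this clause, and Section 6.2.1.6 leaves the final MTD to the DMC and the sponsor. No sample size, power or alpha figure is affected. The amendment is worth making because it is cheap and protects the primary safety endpoint.

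**What to change.** Amend the protocol as follows:

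1. Narrow 9.6.4 so that the exclusion covers only signs and symptoms present at baseline and not worsened in CTCAE grade.
2. Record as an AE any sign or symptom that is new or worsened after the first dose, with the investigator's attribution. Candidate grade ≥2 events in the accelerated stage and candidate events in the DLT window then reach the DMC.
3. Keep the rule that all deaths, including those from progression, are reported as SAEs.
4. Keep the cross-reference in 9.6, pointing to the narrowed exclusion.
5. Reconcile 9.6.4 with 6.2.1.3, 6.2.3 and 9.1, so that one standard decides what is set aside as disease-related.

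Little new machinery is needed. Section 9.6.7 already has a not-related category for events explained by the patient's clinical state, and Section 11.4.3 already plans separate tables for all and for related TEAEs. The cost is a short amendment, more AE entries per patient, and somewhat higher reported all-cause AE rates.

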### **9.6.5 Severity**

The Investigator will use CTCAE version 5.0 to describe the severity of the AE apart from AEs of CRS (see section [9.6.1.1](#)). If the severity changes over the course of the event, the grade assigned by the Investigator should be the most severe that occurred during the AE period. For grading of CRS and neurological AEs please see section [7.2.4](#).

### **9.6.6 Outcome**

The Investigator must judge the outcome of an AE by the following terms

- Recovered
- Recovered with sequelae (description of the sequelae should be provided)
- Not recovered
- Fatal
- Unknown\*

\*Should only be used if the patient is lost to follow-up

### **9.6.7 Relationship to Investigational Medicinal Product**

The Investigator must assess whether the event is related to the IMP.

A suspected adverse drug reaction is defined as one in which there is a reasonable possibility that the IMP caused the AE. Relatedness must be assessed and reported from the first time the AE is being reported. When assessing the causal relationship of an AE to an IMP, the following should be taken into consideration:

#### Not related (unlikely)

The AE is not related to the IMP, which means the AE:

- Does not follow a reasonable temporal sequence from IMP administration
- Is readily explained by the patient's clinical state or by other modes of therapy administered to the patient
- Is clearly not related to the IMP

